#### **6.1.14.4. Electrocardiograms**

In this study, 12-lead ECGs will be obtained in triplicate at defined study visits (Visits 1, 8, 12, and 15/discontinuation), with each measurement done approximately 1 minute apart.

The ECGs recordings will be electronically transmitted to a centralized ECG vendor who will complete the ECG overread. All three of the ECG recordings will be overread by the vendor. For patient management purposes during the study, the vendor will send the study site a full overread/interpretation for only one of the triplicate ECG recordings (the first readable) obtained at each visit. For data analysis purpose, the vendor overread of QT, PR, RR and QRS measurements (the non-missing values) from all 3 ECG recordings will be averaged, and these averaged values will represent the ECG results for each patient/visit. The QTc result for each ECG recording will be determined using the HR, RR and QT intervals and then the average QTc will be calculated.

The incidence of patients meeting criteria for treatment-emergent abnormal values at endpoint (LOCF) and at any time will be summarized for SP II, SP III and SP II/III, and compared between treatment groups for SP II. The abnormality criteria are presented in Table HMGW.6.7. In those analyses, only patients with normal values at all baseline visits with respect to direction being analyzed will be included. The normal limits at baseline are described in Table HMGW 6.8. The Fridericia's corrected QT interval (QTcF) (msec) will be calculated as  $QT/RR^{1/3}$ . The Bazette's corrected QT interval (QTcB) (msec) will be calculated as  $QT/RR^{1/2}$ .

In addition to categorical analyses of the QTc intervals based on absolute values, it is customary (and expected by regulatory bodies, particularly the Committee for Proprietary medicinal Products [CPMP]) that the proportion of subjects with increases from baseline above certain thresholds also be analyzed. These thresholds are based on estimates of normal variance (versus drug-induced changes) in QTc intervals. These thresholds are:

$\geq 30$  msec

$\geq 60$  msec

$\geq 75$  msec

A listing of patients with treatment-emergent abnormal values using the criteria in Table HMGW.6.7 will be presented.

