**Table HMGW.6.1 Patient Population with Baseline and Post-baseline Definitions by Study Period and Type of Analysis**

Study Period / Analysis	Patient Population	Baseline Definition	Post-baseline Definition
Acute Phase			
Efficacy	Patients with a baseline and at least one post-baseline observation	Last of Visits 1-2	All Visits 3-8
TEAEs	All randomized patients	All Visits 1-2	All Visits 2.01-8
SAE and DCAE	All randomized patients	NA	All Visits 2.01-8
C-SSRS categorical analyses	All randomized patients	Lifetime baseline: All Visits 1-2 Lead-in baseline: Visit 2	All Visits 2.01-8
Treatment Emergent Abnormal Labs	Patients with normal laboratory values at all nonmissing baseline visits (with respect to direction being analyzed) and who have at least one post-baseline observation	All of Visits 1-2	All Visits 2.01-8
Treatment emergent low blood pressure	Patients with normal values at all nonmissing baseline visits (with respect to direction being analyzed) and who have at least one post-baseline observation. See Table HMGW.6.4 for normal limits of blood pressure.	Minimum value from Visits 1-2	All Visits 2.01-8
PCS in vital signs, weight, sustained blood pressure analyses	Vital signs: Patients with normal values at all nonmissing baseline visits (with respect to direction being analyzed) and who have at least one post-baseline observation. See Table HMGW.6.4 for normal limits of vital signs. Weight:	Low: Minimum value from Visits 1-2 High: Maximum value from Visits 1-2	All Visits 2.01-8

	Patients with non-missing baseline and at least one post-baseline value.		
Treatment-emergent changes in ECG intervals and heart rate	Patients with normal values at all nonmissing baseline visits (with respect to direction being analyzed) and who have at least one post-baseline observation. See Table HMGW.6.8 for normal limits of ECG.	Low: Minimum value from Visits 1-2 High: Maximum value from Visits 1-2	All Visits 2.01-8
Continuous Safety measures	Patients with a baseline and at least one post-baseline observation	Last of Visits 1-2	All Visits 3-8
Extension Phase			
Efficacy	Patients with a baseline and at least one post-baseline observation	Last of Visits 3-8	All Visits 9-15
TEAEs	All randomized patients entering extension phase	Maximum severity between $7 \leq \text{Visit} \leq 8$	All Visits 8.01-15
SAE and DCAE	All randomized patients entering extension phase	NA	All Visits 8.01-15

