**Table HMGW. 6.7 Criteria to Identify Patients with Treatment-Emergent Abnormalities in ECG.**

Parameter	Low Value	High Value
Heart Rate (bpm)		
Adolescents (13-17)	<50 bpm	>110 bpm
PR Interval	N/A	>220 msec
QRS Interval	N/A	>120msec
QTc Bazett – Female	N/A	$\geq 470$ msec
QTc Bazett – Male	N/A	$\geq 450$ msec
QTc Bazett – Male or Female	N/A	> 40 msec increase from baseline
QTc Fridericia– Female	N/A	$\geq 470$ msec
QTc Fridericia – Male	N/A	$\geq 450$ msec
QTc Fridericia – Male or Female	N/A	> 40 msec increase from baseline

N/A = Not applicable

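### As written, the normal-baseline rule also covers the QTc rows counting increases above 40 msec, leaving patients with a long baseline QTc out of that count (minor)

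*SAP*

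**What the plan says.** Section 6.1.14.4 sets out the treatment-emergent ECG incidence for SP II, SP III and SP II/III, at endpoint and at any time. It states "The abnormality criteria are presented in Table HMGW.6.7" and follows with "In those analyses, only patients with normal values at all baseline visits with respect to direction being analyzed will be included". Normal at baseline is defined in Table HMGW.6.8: QTcB and QTcF below 470 msec for females and below 450 msec for males.

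Table HMGW.6.7 holds two kinds of QTc criterion. One is an absolute limit (at least 470 msec female, at least 450 msec male). The other applies to both sexes and is a change: "> 40 msec increase from baseline". Table HMGW.6.8 has no row for the change criterion, neither a limit nor an exemption.

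Table HMGW.6.1 repeats the restriction in its row for treatment-emergent changes in ECG intervals and heart rate, in the acute, extension and combined phases: "Patients with normal values at all nonmissing baseline visits (with respect to direction being analyzed) and who have at least one post-baseline observation".

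Three other provisions bear on the point:

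- After the absolute-value analyses, Section 6.1.14.4 asks "that the proportion of subjects with increases from baseline above certain thresholds also be analyzed", with thresholds of 30, 60 and 75 msec. That paragraph names no population.
- QTc above 500 msec is counted as potentially clinically significant (PCS) in patients at or below 500 msec at all baseline visits.
- "A listing of patients with treatment-emergent abnormal values using the criteria in Table HMGW.6.7 will be presented".

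**The concern.** A normal-baseline rule is needed when counting new crossings of a limit, because a patient already beyond the limit cannot cross it. A criterion defined by the size of a change has no limit to cross, so the rule only removes patients. Those removed start with the longest QTc, and in them a given rise ends closest to 500 msec.

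The SAP follows the other logic for its weight criterion, a loss of at least 3.5% (Table HMGW.6.6). The population for weight in Table HMGW.6.1 is "Patients with non-missing baseline and at least one post-baseline value", with no normal-baseline condition. No reason is given for treating a QTc change differently.

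At stake are the completeness of one outlier count and its listing, and whether the four increase thresholds (above 40, and at least 30, 60 and 75 msec) are counted in the same patients.

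**Working it through.** There is no planned figure to reproduce, so the check applies the SAP's own cut-offs to a QTc rise above 40 msec.

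**Step 1: who is left out of Table HMGW.6.7.** Under Table HMGW.6.8, males with baseline QTc of 450 msec or more and females with 470 msec or more are left out of both the absolute row and the change row.

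**Step 2: which of these rises the PCS analysis captures.** It needs a baseline of at most 500 msec and a later value above 500 msec.

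- Male, baseline 460 to 500: the rise ends above 460 + 40 = 500, so it is always counted.
- Female, baseline 470 to 500: the rise ends above 470 + 40 = 510, so it is always counted.
- Male, baseline 450 to below 460: the rise ends above 450 + 40 = 490 at the least, so it may end at or below 500 and then is not counted. In whole msec the uncounted rises run from 41 to 50 at baseline 450 and shrink to 41 only at baseline 459.
- Either sex, baseline above 500: excluded from the PCS analysis by its own baseline condition.

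| Baseline QTc (msec), rise above 40 | Table HMGW.6.7 | Above 500 (PCS) |
|---|---|---|
| Male 450 to <460, ends at or below 500 | left out | not counted |
| Male 450 to <460, ends above 500 | left out | counted |
| Male 460 to 500 | left out | counted |
| Female 470 to 500 | left out | counted |
| Either sex above 500 | left out | left out |

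Example: a male going from 455 to 499 msec rises by 499 − 455 = 44. He is in neither Table HMGW.6.7 row and does not exceed 500. If the 30/60/75 analyses are run without restriction, he appears under at least 30 msec only.

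**Step 3: the extension phase.** For SP III the ECG baseline in Table HMGW.6.1 is taken from Visits 2.01 to 8, and the maximum is used for high values. A patient whose QTc first reaches 450 or 470 msec in SP II therefore leaves the SP III count. For patients randomized to placebo, SP III is their first exposure to duloxetine. Section 6.1.2 defines the SP II/III group as those randomized to duloxetine, so the combined-phase count does not recover the placebo patients.

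**Step 4: order of size.** The SAP gives neither a baseline QTc distribution nor a sex ratio. Assume a normal distribution with mean 405 to 425 msec and SD 18 to 22, 15 to 25% males, and 184 randomized patients.

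- Patients left out at baseline = 184 × [male share × P(QTc ≥ 450) + female share × P(QTc ≥ 470)] = 0.2 to 8.7.
- Males in the unrecovered band = 184 × male share × P(450 ≤ QTc < 460) = 0.1 to 3.3 (0.5 to 1.6 at mean 415).
- Baseline above 500 = 184 × P(QTc > 500) = at most 0.06.

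These are patients with such a baseline, not events. The number of missed rises is the last two figures multiplied by the unknown chance of a rise above 40 msec (and, for the male band, of ending at or below 500).

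**The case against.** The strongest reply is that the restriction was never meant for the change rows. Table HMGW.6.8 mirrors every row of Table HMGW.6.7 except the two change rows, so one can argue that no baseline limit exists for them and none applies. Weight fits that reading: it has no normal limit in Table HMGW.6.4 and no normal-baseline restriction. This stands as evidence of intent, but the text does not say it. The restricting sentence covers all analyses using Table HMGW.6.7, and Table HMGW.6.1 restricts the same group with no exemption.

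The second reply is that other analyses cover these patients, and much of it stands. A reader might infer that a large rise from a long baseline vanishes from ECG reporting. The SAP does not support that: the above-500 analysis recovers most such rises, the 30/60/75 paragraph states no restriction, and the ANCOVA of change includes patients with a baseline and a post-baseline value. Two limits remain. The 30/60/75 counts have no named population, and the ECG row of Table HMGW.6.1 could be read as restricting them too. The ANCOVA describes means and does not identify individuals.

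The third reply is that the listing sentence does not repeat the restriction. That is correct. Absence from the listing follows only from the ordinary meaning of treatment-emergent in that section.

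**Conclusion.** The point holds as a minor one. On the plain text of Section 6.1.14.4 and Tables HMGW.6.1 and HMGW.6.8, patients with baseline QTc of at least 450 msec (male) or 470 msec (female) are left out of the incidence of increases above 40 msec and, by the ordinary reading, out of its listing. For SP III this extends to patients who reach those limits during SP II.

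The rises that both the Table HMGW.6.7 and above-500 counts miss are confined to males starting at 450 to below 460 msec who end at or below 500, and to anyone starting above 500. Their number cannot be derived from the SAP and is likely to be very small. A reader might take the 0.2 to 8.7 of 184 as missed safety signals. They are not: that range counts patients with a long QTc before treatment, under assumed distributions, and says nothing about how many then rise by more than 40 msec. The primary analysis is not affected.

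**What to change.** In Section 6.1.14.4, state that the normal-baseline rule applies to absolute limits only: heart rate, PR, QRS, the sex-specific QTc limits of 450 and 470 msec, and the above-500 analysis with its own baseline condition. State also that every QTc increase threshold (above 40, and at least 30, 60 and 75 msec), and the listing of increases above 40 msec, includes all patients with a baseline and at least one post-baseline QTc in the period analysed, whatever the baseline value.

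Add a matching line to Table HMGW.6.1 for the acute, extension and combined phases, modelled on the weight population. The four thresholds then share one denominator.

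The cost is a short addition to the text and one table line per phase. No new data are needed.

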**Table HMGW. 6.7 Criteria to Identify Patients with Treatment-Emergent Abnormalities in ECG.**

Parameter	Low Value	High Value
Heart Rate (bpm)		
Adolescents (13-17)	<50 bpm	>110 bpm
PR Interval	N/A	>220 msec
QRS Interval	N/A	>120msec
QTc Bazett – Female	N/A	$\geq 470$ msec
QTc Bazett – Male	N/A	$\geq 450$ msec
QTc Bazett – Male or Female	N/A	> 40 msec increase from baseline
QTc Fridericia– Female	N/A	$\geq 470$ msec
QTc Fridericia – Male	N/A	$\geq 450$ msec
QTc Fridericia – Male or Female	N/A	> 40 msec increase from baseline

N/A = Not applicable

**Table HMGW.6.8 Normal Limits at Baseline for ECG Analyses**

Parameter	Normal Limits for treatment emergent or PCS Low	Normal Limits for treatment emergent or PCS High

Heart Rate (bpm)		
Adolescents (13-17)	$\geq 50$ bpm	$\leq 110$ bpm
PR Interval	N/A	$\leq 220$ msec
QRS Interval	N/A	$\leq 120$ msec
QTc Bazett – Female	N/A	$< 470$ msec
QTc Bazett – Male	N/A	$< 450$ msec
QTc Fridericia– Female	N/A	$< 470$ msec
QTc Fridericia – Male	N/A	$< 450$ msec
PCS QTc Bazett and QTc Fridericia	N/A	$\leq 500$ msec

The incidence of patients with PCS high QTc Bazett and QTc Fridericia at any time and at endpoint, defined as value greater than 500 msec, will be summarized for SP II, SP III and SP II/III. In these analyses, only patients with a value less than or equal to 500 msec at all baseline visits will be included.

Change from baseline in ECG data will be analyzed using an ANCOVA model with baseline values as covariates for SP II, SP III and SP II/III. Raw values will be used for these analyses unless normality assumptions appear to be violated in which case the data will be rank transformed. These analyses will include summaries of baseline values, endpoint (LOCF) values, and change from baseline to endpoint (LOCF) by treatment group.

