#### 6.1.2. General Considerations

Efficacy and safety analyses will be done on an intent-to-treat (ITT) basis unless otherwise specified. An intent-to-treat analysis is an analysis of data by the groups to which patients are assigned by random allocation, even if the patient does not take the assigned treatment, does not receive the correct treatment, or otherwise does not follow the protocol.

All efficacy and safety analyses of continuous measures will include randomized patients with both a baseline and at least one post-baseline value for the variable being analyzed. For efficacy and continuous safety variables, baseline is defined as the last measurement taken at, or prior to the visit where the study period begins; endpoint is defined as the last non-missing measurement for the study period of interest. Table HMGW 6.1 provides baseline and post-baseline definitions for all variables.

Statistical analyses will be carried out for Study Period II, III, and IV (SP II-IV). All tests of hypotheses will be evaluated based on a two-sided significance level of 0.05 unless otherwise specified. No adjustments for multiple comparisons will be made.

For SP II, a patient's treatment group will be determined by the treatment to which the patient is randomized: either duloxetine (DLX) or placebo (PLA).

For SP III, the following treatment groups will be determined by the randomized treatment at SP II and extension phase treatment at SP III:

PLA/DLX: patients who are randomized to placebo at SP II and who enter SP III and take duloxetine.

DLX/DLX: patients who are randomized to duloxetine at SP II and who enter SP III and take duloxetine.

No statistical comparisons will be conducted to compare the two treatment groups PLA/DLX and DLX/DLX during SP III unless otherwise noted. For continuous measures, when appropriate, within treatment testing of change from baseline for selected safety and efficacy measures will be conducted for SP III.

For SP II/III, one treatment group will be determined by the randomized treatment at SP II:

DLX: patients who are randomized to duloxetine at SPII, including patients who may have discontinued early at SPII or who enter SPIII.

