The same MMRM, ANOVA and ANCOVA models excluding treatment effect will be used to present data for Study Period III, where appropriate.

Unless otherwise specified, for all analyses using the last-observation-carried forward (LOCF) approach in Study Period II, endpoint is defined as the last nonmissing observation obtained from Visit 3 through Visit 8; for the analyses using LOCF in Study Period III, endpoint is defined as the last nonmissing observation from Visit 9 through Visit 15.

In the analyses of some efficacy variables for Study Period II, the baseline-observation-carried-forward (BOCF) approach is considered. The BOCF endpoint is defined as follows:

For randomized patients who complete the treatment period (that is, complete the scheduled Visit 8) and have last nonmissing value at Visit 8, the BOCF endpoint is defined as the last nonmissing observation, for randomized patients who discontinue early (that is, do not complete the scheduled Visit 8) but with at least one non-missing baseline value, the BOCF endpoint is defined as the baseline value.

Categorical comparisons between treatment groups will be performed using Cochran-Mantel-Haenszel (CMH) test controlling for pooled investigative site and Fisher's exact test for Study Period II, when appropriate. For the categorical data, the number and percentage of patients for the categorical variables will be presented for Study Period III.

Where appropriate, variables will be summarized descriptively (frequency and percent will be summarized for categorical variables; number of patients with a non-missing observation, mean, SD, median, minimum, and maximum will be summarized for continuous variables) by study visit.

For those data summaries accompanied by individual patient data listings, data will be sorted by investigator ID, patient ID, and visit or event number if it is available.

Changes made to the data analysis methods will not necessarily require a protocol amendment and will be described in an updated SAP and reflected in the final report.

Statistical analysis of this study will be the responsibility of Eli Lilly and Company or designee. SAS® software will be used to perform most or all statistical analyses.

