### **6.1.3. Adjustments for Covariates**

In general, when a repeated measures analysis is used, the model will include the fixed categorical effect of treatment, pooled investigative site, visit, treatment-by-visit interaction, and the continuous, fixed covariates of the baseline value of the variable being analyzed and baseline value of the variable being analyzed-by-visit interaction. The baseline value of the variable being analyzed and the baseline value of the variable being analyzed-by-visit interaction are included to account for the differing influence over time of the baseline score on the post-baseline scores.

When an analysis of covariance (ANCOVA) model is used to analyze a continuous variable, the model will contain the main effects of treatment, pooled investigative site, and appropriate baseline values included as covariates.

Data presentations for Study Period III will be based on the same MMRM and ANCOVA models excluding treatment effect, where appropriate.

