#### **6.1.14.2. Clinical Laboratory Evaluation**

The incidence rates of patients with treatment-emergent abnormal, high or low laboratory values at endpoint (LOCF) will be summarized for SP II, SP II and SP II/II, and compared between treatment groups for SP II. Listings of abnormal lab values and treatment-emergent abnormal lab values will also be presented.

A “treatment-emergent abnormal value at endpoint” is defined as a change from normal at all visits during baseline to abnormal at endpoint. A “treatment-emergent high value at endpoint” is defined as a change from a value less than or equal to the high limit at all visits during baseline to a value greater than the high limit at endpoint. A “treatment-emergent low value at endpoint” is defined as a change from a value greater than or equal to the low limit at all visits during baseline to a value less than the low limit at endpoint. High and low reference ranges for adolescent patients will be used to determine treatment emergent abnormal, high, low values. These reference ranges will be provided by a central laboratory. The same analysis will be done for “treatment-emergent abnormal value at anytime”, “treatment-emergent high value at any time”, and “treatment-emergent low value at any time”.

Treatment emergent liver function abnormalities at any time post-baseline for patients with normal ALT values (ALT <1 time upper limit normal) at last non-missing baseline will be summarized for SP II, SP III and SP II/III, and compared between treatment groups for SP II for the following categories:

ALT  $\geq$  3 times upper limit normal

ALT  $\geq$  5 times upper limit normal

ALT  $\geq$  10 times upper limit normal

Hy's Rule, ALT  $\geq$  3 times upper limit normal and total bilirubin  $\geq$  2 times upper limit normal.

A listing of patients with ALT  $\geq$  3 times upper limit normal at any time during post-baseline will be presented. And, a listing of all laboratory values will be presented.

For the continuous laboratory analytes, change from baseline to endpoint will be assessed using an ANOVA model (see Section 6.1.2 and 6.1.3) for Study Period II, and will be summarized for Study Period III and Study Period II/III. Rank transformed data for lab analytes will be used for the laboratory analysis. Within treatment testing of change from baseline will be based on a Wilcoxon Signed-Rank Test.

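### The rank fallback for ECG change also covers SP III and SP II/III, where the ANCOVA has no treatment term and a ranked model cannot show whether the ECG changed

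*SAP*

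**What the plan says.** SAP Section 6.1.14.4 (text after Table HMGW.6.8) says that ECG change "will be analyzed using an ANCOVA model with baseline values as covariates for SP II, SP III and SP II/III". The next sentence is the fallback: "Raw values will be used for these analyses unless normality assumptions appear to be violated in which case the data will be rank transformed". It refers to all the analyses just listed and is not confined to SP II. The section adds: "These analyses will include summaries of baseline values, endpoint (LOCF) values, and change from baseline to endpoint (LOCF) by treatment group".

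The general ANCOVA is set out in Section 6.1.3: "the model will contain the main effects of treatment, pooled investigative site, and appropriate baseline values included as covariates". For the extension, Section 6.1.2 says: "The same MMRM, ANOVA and ANCOVA models excluding treatment effect will be used to present data for Study Period III, where appropriate". For the combined period it says: "For SP II/III, one treatment group will be determined by the randomized treatment at SP II". That group is the patients randomized to duloxetine.

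Section 6.1.14.3 repeats the fallback sentence for the ANCOVA of vital signs, weight and height. It then plans an MMRM for blood pressure, pulse and weight in the same three periods, with within-treatment testing.

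Section 6.1.14.2 ranks laboratory analytes too, but protects the one-group question: "Within treatment testing of change from baseline will be based on a Wilcoxon Signed-Rank Test".

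**The concern.** A rank transform is a reasonable device for comparing two arms, because the question is which arm holds the higher ranks. SP III and SP II/III ask a different question: did the ECG change from baseline in treated patients? Ranking the changes removes their zero point and their unit. With no treatment term, the model then has nothing to estimate that bears on that question.

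For ECG this ANCOVA is the only model of continuous change. If normality appeared violated, the modelled long-term result for QTc, PR, QRS and heart rate would be uninformative. A reader could also mistake a mean rank far from zero for a drug effect.

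**Working it through.** The SAP gives no figure on this point, so there is none to reproduce.

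**Inputs.** Section 5.2 gives 184 patients randomized 1:1, so 184/2 = 92 per arm, and about 81% completing SP II. That is 0.81 × 92 = 74.5 per arm and 0.81 × 184 = 149 in all entering SP III. n = 92 for SP II/III assumes that every duloxetine patient has a baseline and a post-baseline ECG.

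**Closed form.** Untied ranks 1 to n have mean (n+1)/2 and sample variance n(n+1)/12. The standard error of the mean is therefore √((n+1)/12), and a one-sample t against zero is

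t = [(n+1)/2] / √((n+1)/12) = √(3(n+1)).

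The measured changes do not appear in this expression.

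| n | mean rank | t against 0 |
|---|---|---|
| 74 | 75/2 = 37.5 | √225 = 15.0 |
| 92 | 93/2 = 46.5 | √279 = 16.7 |
| 149 | 150/2 = 75.0 | √450 = 21.2 |

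Such a test gives p = 0.074 at n = 3 and p = 0.030 at n = 4. It is below 0.05 for every n of 4 or more.

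**With site and baseline in the model.** The simulation used 500 data sets per setting. Its assumptions, which are not in the SAP, were t errors with 3 degrees of freedom and scale 9 msec; 12, 15 and 20 pooled sites for n = 74, 92 and 149; and true common shifts of −30, −10, 0, +10 and +30 msec.

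- Adjusted mean rank with observed site weights: exactly (n+1)/2 in every run.
- Adjusted mean rank with equal site weights (the usual LSMean): only centred there. At n = 92 it averaged 46.4 (range 42.4 to 51.2); at n = 149, 75.0 (range 68.7 to 83.9).
- Both were identical at all five shifts, and a test against zero rejected in 100% of runs.
- The same model on raw values at n = 92 averaged −29.99, −9.99, 0.01, 10.01 and 30.01 msec, so it tracks the truth.
- The signed-rank test at zero shift rejected in 2.8%, 4.8% and 6.0% of runs (n = 74, 92, 149), and in 100% at ±10 and ±30 msec.

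**Ranks pooled over both SP III groups but shown by group.** With 74 and 75 patients, SD 15 msec (assumed) and a 10 msec difference between groups, the mean ranks were 88.4 and 61.8, around 75 overall. The groups separate, but a shift common to both still does not show.

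**The case against.** The strongest reply is that little depends on this model. Section 6.1.14 limits SP III safety to descriptive statistics. Section 6.1.14.4 also asks for summaries of baseline, endpoint and change by group, and nothing says these must be of ranks. Treatment-emergent abnormalities and QTc above 500 msec are planned for SP III and SP II/III, and categories of QTc increase are defined as well, all in original units. A large QTc shift would therefore be seen. This stands, and it is why the point is minor.

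Three stronger readings are tempting but not supported.

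- *That the plan will produce a falsely significant ECG result.* Section 6.1.14.4 names no test against zero. Section 6.1.2 allows within-treatment tests for selected measures where appropriate and does not name ECG. The false significance follows only if such a test were run on the ranks.
- *That the adjusted mean is exactly (n+1)/2.* This is exact for the plain or observed-weight mean. It is approximate for equal-weight LSMeans, and group means can depart from it if ranks are pooled over both SP III groups.
- *That blood pressure, pulse and weight lose their modelled change as well.* The MMRM in Section 6.1.14.3 supplies it in all three periods, and the fallback sentence belongs to the ANCOVA paragraph before it.

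None of this makes the ranked one-group model informative.

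**Conclusion.** The point holds, at minor severity. As written, the fallback reaches SP III and SP II/III, where no treatment contrast exists. If triggered there, the only model of continuous ECG change returns about (n+1)/2, or 46.5 for n = 92, at any true change. The same applies to the vital-signs ANCOVA, where only height lacks another model. What is lost is the modelled ECG result, not the ECG evidence as a whole.

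The conclusion rests on reading the fallback as covering every period listed in the sentence before it, and on the treatment effect being left out in SP III as Section 6.1.2 directs. The invariance itself is algebraic; the simulation assumptions affect only the spread of the equal-weight LSMeans and the rejection rates of the comparison tests. In SP II the ranked between-treatment test is valid and is not part of this criticism.

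**What to change.** In Sections 6.1.14.4 and 6.1.14.3, state that:

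- rank transformation applies only to the between-treatment comparison in SP II;
- change from baseline in SP III and SP II/III is summarized and modelled on the raw scale;
- if a within-treatment test is wanted and normality is doubtful, it is the Wilcoxon signed-rank test on the changes, as Section 6.1.14.2 already does for laboratory data.

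The cost is two or three sentences of SAP text and a standard procedure. No new data are needed.
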